6.2.10. PF-07321332 Plasma PK in Plasma and Whole Blood (if feasible)

The PK analyses will be performed and summarized by the PK/PD group.

6.2.11. Viral Titers Measured via RT-PCR in Nasal Swabs Over Time

The viral load data measured in Day 1 and Day 5 are nasopharyngeal samples. These are the samples that will be used on the POC analysis. POC analysis of viral load data will occur when approximately 200 participants in the mITT population with evaluable data complete the Day 5 assessments.

Descriptive statistics by treatment group for the change from baseline will be provided. An analysis of covariance (ANCOVA) model will be used to analyze the change from baseline in Log10 transformed viral load (copies/mL) data. The ANCOVA model will include treatment group, baseline viral load and baseline serology status. The mAb treatment (yes/no) as well as symptom onset to first dose date (\leq 3 days, >3 days) will be used in the model dependent of population. Participants are excluded from the analysis for reasons of Not Detected, Zero or Missing baseline viral load result, and local (nonvalidated) swabs use. Results from samples collected at non-nasopharyngeal site (like nostril, other or missing) are also excluded. As well as exclusions due to non-validated swab use (only viral load data based on samples collected through validated swab will be used for analyses). In addition, a sensitivity analysis summaries will be performed excluding all data from India sites.

The viral load measured in nasal or nasopharyngeal samples over time will be evaluated. The change from baseline to each visit (Day 3, Day 5, Day 10, Day 14) in viral load will be analyzed using an MMRM method. Viral load, including change from baseline, will be summarized by treatment group. Change from baseline to Day 3/Day 5/Day 10/Day 14 in viral load in the log base 10 scale will be statistically analyzed using a linear mixed-effect model. The model will contain log base 10 transformed baseline as a covariate, baseline serology status, treatment, day, treatment-by-day as fixed effects. Sampling site (Nasopharyngeal or not) will be included as covariate in the model if applicable. The mAb treatment (yes/no) as well as symptom onset to first dose date (\leq 3 days, >3 days) will be used in the model dependent of population. The LS means and treatment difference will be calculated and presented with their corresponding 95% CIs. The analyses will be done using mITT, mITT1 and mITT2 populations.

In the mITT and mITT1 populations, the analysis will be repeated in subgroups based on baseline serology status (positive, negative), by baseline viral load ($<10^4$ copies/mL, $\ge 10^4$ copies/mL) and ($<10^7$ copies/mL, $\ge 10^7$ copies/mL).

To assess the association between baseline viral strain and primary endpoint, the proportion of participants with primary endpoint events will be summarized according to COVID-19 variants of concern and variants of interests.

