3.5. Stratification Variables

Randomization will be stratified by geographic region and whether participants had received or were expected to receive COVID-19 therapeutic mAb treatment (yes/no) based on the site investigator's assessment at the time of randomization. Randomization for the strata where participants had received or were expected to receive COVID-19 therapeutic mAb treatment will be capped at a maximum of 25% enrollment. Unless otherwise indicated analyses will include calculated values for quantitative stratification variables. Geographical region is defined as follows:

- US region: country of the United States, including Puerto Rico.
- Europe region: countries of Bulgaria, Czech Republic, Hungary, Netherlands, Poland, Spain, and Ukraine.
- Brazil region: country of Brazil.
- India region: country of India.
- Rest of the World region: countries of Argentina, Colombia, Japan, Malaysia, Mexico, Peru, Russian Federation, South Africa, Republic of Korea, Taiwan, Thailand, and Turkey.

If a region enrolled <10 participants, the region will be combined with the "rest f the word" region.

Baseline and stratification variables above defined will be applied to the analyses depending on the analysis population used:

- mITT analyses will include the following stratification variables: Baseline viral load, baseline serology status, geographic region.
- mITT1 analysis will include: Baseline viral load, baseline serology status, geographic region and symptom onset days to first dose date (≤3 days, >3 days).
- mITT2 analyses will include: Baseline viral load, baseline serology status, geographic region, received or were expected to receive mAb treatment (yes/no) and symptom onset days to first dose date (≤3 days, >3 days).

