6.2.12. Number of COVID-19 Related Medical Visits

The number of COVID-19 related medical visits will be analyzed with a negative-binomial regression model, using the log-total number of days of data collection as the participant offset variable. The resulting analysis will show the difference in estimated rate of medical visits between treatment groups. The analyses will be done using mITT, mITT1, and mITT2 populations.

6.2.13. Number of Days in Hospital and ICU Stay in Participants with COVID-19 Related Hospitalization

Health resource utilization data will be summarized by treatment group. This will include number (days) of hospital stay and number (days) of ICU stay. The analyses will be done using mITT, mITT1 ,and mITT2 populations. Descriptive statistics (ie, mean, median, range) will be used to summarize this endpoint.

CCI			

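### The medical-visits count model names no covariates and the viral-load models omit region, although SAP 3.5 sets a covariate list for each analysis set; some precision may be lost

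*SAP*

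**What the plan says.** SAP 3.5 gives a general rule: "Baseline and stratification variables above defined will be applied to the analyses depending on the analysis population used". It then lists the variables set by set. For the primary set, "mITT analyses will include the following stratification variables: Baseline viral load, baseline serology status, geographic region". mITT1 adds symptom-onset group (up to 3 days, or more), and mITT2 adds both onset group and mAb. Only region and mAb were used to stratify randomization; the others are baseline variables.

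**Viral load (SAP 6.2.11).** For the change-from-baseline ANCOVA, "The ANCOVA model will include treatment group, baseline viral load and baseline serology status". The next sentence says that mAb and onset group "will be used in the model dependent of population". For the mixed model, "The model will contain log base 10 transformed baseline as a covariate, baseline serology status, treatment, day, treatment-by-day as fixed effects", with sampling site where applicable and the same provision for mAb and onset group. Region appears in neither. The two viral-load rows of Appendix 1 name only continuous baseline viral load.

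**Medical visits (SAP 5.2.4 and 6.2.12).** The count "will be analyzed with a negative-binomial regression model, using the log-total number of days of data collection as the participant offset variable". No covariate or stratification factor is named. SAP 5.1 puts this endpoint third among the three tested by the Hochberg procedure. Its Appendix 1 row describes the analysis as descriptive statistics based on the negative binomial distribution and does not refer to Section 3.5.

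By contrast, the logistic model (SAP 6.1.1.2) and the Cox model (SAP 6.2.4) name region and point to Section 3.5, as do the logistic and Cox rows of Appendix 1.

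**The concern.** There are two issues.

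The first is prespecification. Medical visits is a formally tested endpoint. One programmer working from SAP 3.5 and another working from SAP 6.2.12 would fit different models and report different p-values, and each could cite the SAP.

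The second is precision. If a factor that was balanced by stratified randomization predicts the outcome and is left out of the model, its between-stratum variation stays in the residual and the standard error is larger than it need be. The documents make this plausible. Protocol 2.2 describes mAbs as intravenous, with monitoring for at least 1 hour after infusion. Protocol 8.1.2 counts office, urgent-care and home-healthcare contacts as COVID-19-related medical visits, so mAb use could itself change the count. Protocol 4.2 says that mAb access outside the US depends on availability. For viral load, SAP 6.2.11 already plans a sensitivity analysis without the India sites, so it treats geography as potentially relevant. None of this shows how strong the effects are.

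**Working it through.** **1. Rule against model**

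| Variable in SAP 3.5 | Sets | Viral-load ANCOVA and mixed model | Medical-visits model |
|---|---|---|---|
| Baseline viral load | all | yes | not named |
| Serology | all | yes | not named |
| Region (randomization factor) | all | **not named** | not named |
| Onset group | mITT1, mITT2 | yes | not named |
| mAb (randomization factor) | mITT2 | yes | not named |

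**2. Figures in the documents.** None bears directly on either model: no SD, visit rate, dispersion or power is given for these endpoints. The primary sample size does reproduce. For 7% versus 3.5%, two-sided 5% and 90% power, the two-proportion formula gives 852 per arm, or 1704 in total, and power at 1717 is 90.2%. Here 1717 serves only as a full-trial n, and about 200 (SAP 6.2.11, proof of concept) as a small n. All other inputs below are assumptions.

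**3. Adding region to the viral-load ANCOVA.** Let R² be the share of residual variance that region explains, and d its degrees of freedom (3 or 4, depending on whether regions are combined). The model without region has 4 parameters: intercept, treatment, baseline and serology.

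SE with region / SE without = √[(1 − R²)(n − 4)/(n − 4 − d)]

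| R² (assumed) | n = 200 | n = 1717 |
|---|---|---|
| 0 | 1.008–1.010 | 1.001 |
| 0.02 | 0.998–1.000 | 0.991 |
| 0.05 | 0.982–0.985 | 0.976 |
| 0.10 | 0.956–0.959 | 0.950 |
| 0.15 | 0.929–0.932 | 0.923 |

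Break-even is at about R² = d/(n − 4). At n = 200 this is 3/196 = 1.5% to 4/196 = 2.0%; below it, adding region widens the standard error by at most 1%. At n = 1717 and R² = 0.15 the reduction is about 8%. The same ratio approximates the mixed model at a single visit.

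**4. Adding the SAP 3.5 list to the count model, by formula.** Per participant, the variance of an arm's log rate is about 1/μ + k, with mean count μ and dispersion k. If covariates explain a share f of the between-participant variance, k becomes k(1 − f).

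SE adjusted / SE unadjusted = √[(1/μ + k(1 − f))/(1/μ + k)]

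- Least gain (μ = 0.05, k = 1, f = 0.05): √(20.95/21) = 0.999.
- Middle (μ = 0.1, k = 5, f = 0.2): √(14/15) = 0.966.
- Most gain (μ = 0.3, k = 10, f = 0.3): √(10.33/13.33) = 0.880.

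The reduction is therefore about 0 to 12%.

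**5. The same by simulation.** Settings: 1716 participants, four regions with stratified randomization, k = 3, rate ratio 0.7, mean 0.1 or 0.3, about 150 replicates per scenario. The ratio of model-based standard errors (adjusted/unadjusted) was 1.000–1.001 with non-prognostic covariates, 0.995–0.998 with weak ones and 0.976–0.989 with moderate ones, a reduction of 0 to about 2.5%. The ratio of empirical SDs ran from 0.947 to 1.015, which is too noisy at 150 replicates to refine this. Mean log rate ratios were −0.347 to −0.366 in both models, against ln 0.7 = −0.357, so adjustment did not visibly shift the estimate.

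**6. Single factors, with larger assumed effects** (200 to 250 replicates, k = 0.7 to 1.0; ratios here are unadjusted/adjusted).

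- mAb in mITT2, 20% on mAb: 1.009 for rates 0.2 versus 0.4, 1.077 for 0.2 versus 1.0, and 1.078 for 0.3 versus 1.3.
- Region in mITT: 1.005 for a 2-fold spread in rates, and 1.013 to 1.049 for a 4-fold spread.

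**The case against.** The best defence is that SAP 6.2.12 is silent rather than contrary. It names a model family and an offset and does not say the model is unadjusted. If the general rule in SAP 3.5 governs, the covariates are already in. If Appendix 1 governs, Section 3.5 applies only where a row invokes it. The SAP version history also lists the sections to which the Section 3.5 clarification was added, and 6.2.12 is not among them. This stands to the extent that the defect may be unclear scope rather than outright contradiction. It does not remove the need for a change, because both readings are open for a tested endpoint.

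A reader who stops at the quoted ANCOVA sentence might infer that the viral-load models drop covariates and randomization factors generally. They do not: the sentence that follows adds mAb and onset group, and only region is missing. Nor does a confirmatory test depend on those models. Viral load is outside the Hochberg list, and Appendix 1 labels the Day 1 to Day 5 ANCOVA a proof-of-concept sensitivity analysis.

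A reader might also infer that the standard errors are demonstrably too wide. The documents cannot show that; every size above rests on assumed rates and effects, and zero is within range.

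Finally, adjustment is not automatically free. SAP 6.2.11 anticipates missing baseline viral load, and Appendix 1 rules out imputation for medical visits, so a complete-case adjusted model would lose participants. That objection is sound, and the fix has to deal with it.

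**Conclusion.** The point holds as a low-cost improvement. SAP 3.5 is not carried through to the medical-visits model, which names none of its variables, or to the viral-load models, which lack region. The count model matters more, because its p-value enters the Hochberg procedure and its covariate list should be settled in advance whatever precision is gained.

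The size is modest and conditional on the variables being prognostic. The upper ends, 12% for the count model and 8% for region in viral load, need strong assumptions (dispersion 10 with 30% of between-participant variance explained; region explaining 15% of residual variance).

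Two further inferences should be resisted. The omission does not invalidate the tests: leaving out a stratification factor tends to make them conservative. And the mAb gain does not carry over to the primary set, because mITT and mITT1 exclude participants who at baseline had received or were expected to receive mAb; it exists only in mITT2, and SAP 5.1 does not assign the Hochberg tests to mITT2.

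**What to change.** - **SAP 5.2.4 and 6.2.12:** for medical visits, write out the full SAP 3.5 list for each set: baseline viral load, serology and region in all three; onset group as well in mITT1 and mITT2; mAb as well in mITT2. Use a missing category for serology and for baseline viral load so that no participant is dropped, and say in which form viral load enters.
- **SAP 6.2.11:** add region to the ANCOVA and to the mixed model.
- **Appendix 1:** give the medical-visits and viral-load rows the same pointer to Section 3.5 that the logistic and Cox rows carry, and label the medical-visits row as a negative-binomial model rather than descriptive statistics.

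The cost is SAP wording and a few model terms. The variables are already collected, and no visit, sample-size or testing-order change follows. At about 200 participants the worst case is a standard error about 1% wider if region turns out not to be prognostic.

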FSH	X											
 
FSH is to be performed in female participants <60 years of age at screening who are not using hormonal contraception or hormonal replacement therapy, to confirm postmenopausal status. Female participants age 50 to 60 years with no menses for 12 months do not need FSH testing to be performed to confirm postmenopausal status.
 
When FSH testing is required to confirm postmenopausal status, a participant may be enrolled in the study prior to the test result being available as long as the FSH test result confirms postmenopausal status prior to dosing.
 
See Section 10.4.3 and Appendix 2.
 

Rapid antigen testing	X											
 
Only required if a participant does not have results of a positive SARS-CoV-2 test that was obtained within 5 days prior to randomization.
 
Refer to Section 5.1.
 

Viral load assessment		X	X	X	X	X						
 
At baseline, an NP swab will be collected by the investigational site staff to confirm SARS-CoV-2 infection by RT-PCR. This test will not be used to determine study eligibility. Subsequent NP or nasal swabs will be collected on Days 1, 3, 5, 10, and 14.
 
NP swabs will be collected by an HCP during an in-person visit. Otherwise, a nasal
 

Visit Identifier Abbreviations used in this table may be found in Appendix 12.	Screening	Baseline (Day 1)	Day 3	Day 5	Day 10	Day 14	Day 21	Day 34	LT Week 12	F/U Week 24	ET (prior to Day 34)	Notes
Visit Window	Day -1 to Day 1	0 days	±1 day	±1 day	±1 day	±2 days	±2 days	±3 days	±7 days	±7 days	±5 days	
CCI								- V				

swab will be self collected by the participant.

See Section 8.6.4.

		- I -										
PK												
PK sample (PF-07321332)		Х		X								
 
On Day 1, one blood sample for PK will be collected 30 to 90 minutes postdose if feasible for the participant to remain at the site.
 
On Day 5, one blood sample for PK will be collected. The preferred time of sample collection is predose up to 2 hours before study intervention administration; if a predose sample collection is not possible, collect this sample at anytime during the visit, even after study intervention has been administered.
 
Refer to Section 8.4.
 

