- For Study Intervention Administration: Participants will receive study intervention for 5 days (10 doses total). The first dose will be administered at the Baseline/Day 1 visit during the in-person visit, if possible. All subsequent doses (ie, 9) will be self-administered outside the study clinic (eg, at home).
- Screening, Baseline, and Day 5 visits will be conducted in-person (at the investigational site approved by the investigator or a remote location, including a participant's home).
- Day 3 must be conducted in-person for the first 60 participants (sentinel cohort) and thereafter only if a PK sample (not using Tasso) is collected by an HCP or if ECG is required.
- Day 3 and Day 5 visits should be conducted on separate calendar days.
- Day 10, Day 21, Week 12 and Week 24 visits will be conducted by telemedicine system. Telemedicine visits may be converted to an in-person visit at the discretion of the investigator.
- Day 14 visit must be conducted in-person for the first 60 participants (sentinel cohort). Thereafter the visit may be conducted in-person or by telemedicine. After the sentinel cohort the visit must be conducted in person only if ECG is required.
- Day 34 visit will be conducted in-person or by telemedicine system.
- Early Termination prior to Day 34 visit will be conducted in-person or by telemedicine system.

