•	To describe the viral load in nasal samples over time in nonhospitalized symptomatic adult participants with COVID-19 who are at increased risk of progression to severe disease.	
 
Viral titers measured via RT-PCR in nasal swabs over time.
 
	• Not applicable.

Objectives		Endpoints	Estimands
•	To compare PF-07321332/ritonavir to placebo for COVID-19-related medical visits in nonhospitalized symptomatic adult participants with COVID-19 who are at increased risk of progression to severe disease.	• Number of COVID-19 related medical visits through Day 28.	• Not applicable.
•	To compare PF-07321332/ritonavir to placebo for COVID-19-related hospitalizations in nonhospitalized symptomatic adult participants with COVID-19 who are at increased risk of progression to severe disease.	• Number of days in hospital and ICU stay in participants with COVID-19 related hospitalization.	• Not applicable.

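### Viral load change is taken from a nasopharyngeal baseline although later specimens vary with visit mode, so unsplit summaries can show a specimen difference as viral decline

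*SAP*

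**What the plan says.** Protocol 1.3 ties the swab to the visit mode. For the first sample: "At baseline, an NP swab will be collected by the investigational site staff to confirm SARS-CoV-2 infection by RT-PCR". After that, "NP swabs will be collected by an HCP during an in-person visit"; at any other visit a nasal "swab will be self collected by the participant". The schedule footnotes then set the modes:

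- Day 5 is in person.
- Day 10 is remote: "Day 10, Day 21, Week 12 and Week 24 visits will be conducted by telemedicine system". The investigator may convert such a visit to in-person.
- Day 3 is in person for the 60-participant sentinel cohort and "thereafter only if a PK sample (not using Tasso) is collected by an HCP or if ECG is required".
- Day 14 is in person for the sentinel cohort. Later participants may have either mode, unless an ECG is required.

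SAP 6.2.11 agrees about the NP days: "The viral load data measured in Day 1 and Day 5 are nasopharyngeal samples". It then plans three analyses:

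- an ANCOVA of change from Day 1 to Day 5, which drops results from any non-NP site;
- summaries by treatment group of viral load and its change from baseline, with no split by specimen;
- a mixed model of change at Days 3, 5, 10 and 14 that pools both specimen types, with treatment, day and their interaction. On specimen it says: "Sampling site (Nasopharyngeal or not) will be included as covariate in the model if applicable". There is no site-by-day term.

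The endpoint in Protocol section 3 is worded as "Viral titers measured via RT-PCR in nasal swabs over time", under an objective to describe viral load over time. SAP Appendix 1 labels the mixed model the secondary analysis and the ANCOVA a sensitivity (proof-of-concept) analysis.

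**The concern.** No nasal baseline is planned. On a nasal day, change from baseline is therefore viral decline plus whatever difference exists between the two sampling sites. At Day 5, with NP at both ends, it is decline alone. A curve through Days 3, 5, 10 and 14 would then switch specimen along its length and could show steps that have nothing to do with the virus. The SAP itself treats the specimens as not interchangeable, since its ANCOVA excludes non-NP results.

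The mixed model may or may not repair this. The SAP does not say when the site term applies, whether site is coded per sample, or at which site value the LS means are computed. Because the objective is descriptive, the within-arm levels and their course over time are what will be read, and these are what the specimen change affects.

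**Working it through.** The documents give no effect size, SD or NP-to-nasal offset for viral load, so there is no planned figure to reproduce.

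**Inputs from the documents.** Specimen by visit, as set out above. The sentinel cohort is 60 of about 3000 participants: 60/3000 = 2%.

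**Assumptions, not in the documents.** Offset δ (nasal minus NP, log10 copies/mL) = -0.5, -1.0 or -1.5. Nasal share q = 0.90, 0, 1.00 and 0.60 at Days 3, 5, 10 and 14. A positive δ would reverse every sign below.

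**Step 1: summaries without a specimen split.** Expected change on day d = NP change(d) + q(d) × δ. The error is the second term:

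| δ | Day 3 | Day 5 | Day 10 | Day 14 |
|---|---|---|---|---|
| -0.5 | -0.45 | 0 | -0.50 | -0.30 |
| -1.0 | -0.90 | 0 | -1.00 | -0.60 |
| -1.5 | -1.35 | 0 | -1.50 | -0.90 |

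A simulation (correlated repeated measures, 2000 participants, 200 replicates) fitted without a site term agreed to within 0.01. This step needs no assumption about software, only a nonzero δ.

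**Step 2: mixed model with one additive site term and constant δ.** LS mean(d) = NP change(d) + w × δ, where w is the nasal weight used in forming LS means. The shift is the same on every day, including the all-NP Day 5:

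| LS means evaluated at | w | δ = -0.5 | δ = -1.0 | δ = -1.5 |
|---|---|---|---|---|
| NP | 0 | 0 | 0 | 0 |
| equal site weights | 0.5 | -0.25 | -0.50 | -0.75 |
| observed nasal share | (0.90 + 0 + 1.00 + 0.60)/4 = 0.625 | -0.31 | -0.62 | -0.94 |

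The observed share is itself uncertain. With Day 10 all nasal and Day 5 all NP, it is (0.98 + 0 + 1 + 0.98)/4 = 0.74 if Days 3 and 14 are each 98% nasal, and (0.50 + 0 + 1 + 0)/4 = 0.375 if Day 3 is 50% and Day 14 is 0%.

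**Step 3: offset that varies by day.** Take δ = -1, -1, -0.3 and -0.3 at the four visits. The single site coefficient was estimated at -0.49. Evaluated at NP, the remaining error is q(d) × (δ(d) + 0.49):

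- Day 3: 0.90 × (-0.51) = -0.46 (simulated -0.45)
- Day 5: 0
- Day 10: 1.00 × 0.19 = +0.19
- Day 14: 0.60 × 0.19 = +0.11 (simulated +0.12)

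A site-by-day term cannot cure this, because it is not estimable where one specimen is absent (Day 5, and in effect Day 10).

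**Step 4: treatment difference.** In every scenario above, with or without the site term, bias in the between-arm difference was at most 0.01 log10. These runs took specimen mix and offset to be the same in both arms.

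**The case against.** The strongest reply is that the SAP does not specify a wrong analysis. It includes a site covariate and is merely silent on a reporting setting, and with LS means evaluated at NP and a constant offset the error is zero. The offset, its sign and the specimen shares are not in the documents. The randomised comparison is intact, viral load is in neither the sequential tests nor the Hochberg list of SAP 5.1, and the NP-only ANCOVA, planned for mITT, mITT1 and mITT2, already gives a clean Day 5 result.

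Most of that stands, and it rules out four stronger readings that a reader might infer:

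- That the reported declines are wrong even at Day 5. Averaging LS means over site is one possible setting, not SAP text.
- That the post-baseline samples are mostly nasal. Nasal is the default at Day 10 and likely at Day 3. Day 5 is NP and the Day 14 share is undetermined.
- That the treatment effect is biased. Step 4 shows otherwise under balance.
- That the mixed model should be replaced by separate models for each specimen. Splitting Day 14 would compare subsets defined by visit mode after randomisation. Protocol 1.3 requires Day 14 laboratory tests only after an earlier clinically relevant abnormality, so in-person attendance may be related to outcome.

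The reply does not cover the unsplit summaries in Step 1, which carry the offset whatever is done in the model. Nor does an unbiased treatment difference meet an objective that is to describe viral load over time. The ANCOVA covers Day 5 only, and Appendix 1 does not make it the main analysis.

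**Conclusion.** The point holds for the within-arm declines and the time profile. As written, summaries of change from baseline mix viral decline with any NP-to-nasal offset on nasal days and not at Day 5. An all-nasal Day 10 is shifted by the whole offset, so by -0.5 to -1.5 log10 over the assumed range.

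For the mixed model the conclusion is conditional. Within-arm LS means shift by the nasal weight times the offset on every day: -0.25 to -0.75 log10 at equal weights, zero at NP if the offset is constant, and part of the error remains if it varies by day. The SAP does not say which applies.

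The randomised difference is essentially unaffected provided that specimen mix and offset are balanced across arms. The primary endpoint and the tests listed in SAP 5.1 are not touched. This is worth correcting because the affected quantity is the one the objective asks for, and the correction is cheap.

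**What to change.** In SAP 6.2.11 and Appendix 1:

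- Present descriptive viral load and change from baseline by specimen type, and do not join NP and nasal means in one trajectory. Label the Day 14 specimen groups as descriptive only.
- Delete the closing condition on the site covariate, code site per sample, and evaluate the mixed model's LS means at NP. State that this assumes an offset that is constant over days.
- Name the NP-only ANCOVA as the reference for the Day 5 decline.
- Keep all samples in the mixed model for the treatment difference; do not split Day 14 by specimen.

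In both documents, reword the endpoint to nasopharyngeal or nasal swabs.

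The cost is wording and a re-cut of tables from data already being collected. The downside is that there will be no single pooled curve of change from baseline.
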